#### Mumps Per-Protocol Analysis Set (mumps-PP)

The mumps-PP analysis set will be based on participants who meet all of the following criteria:

- Fulfilled the eligibility (inclusion/exclusion) criteria.
- Received all study vaccines as assigned.
- Provided a valid mumps serology laboratory result at baseline and at 56 days postvaccination with MMR vaccine, with specimens taken within the windows indicated in Table 1.
- Did not take any prohibited concomitant medication within 28 days post-vaccination.
- Did not show seropositivity for mumps at baseline.

## Rubella Per-Protocol Analysis Set (rubella-PP)

The rubella-PP analysis set will be based on participants who meet all of the following criteria:

- Fulfilled the eligibility (inclusion/exclusion) criteria.
- Received all study vaccines as assigned.
- Provided a valid rubella serology laboratory result at baseline and at 56 days postvaccination with MMR vaccine, with specimens taken within the windows indicated in Table 1.
- Did not take any prohibited concomitant medication within 28 days post-vaccination.
- Did not show seropositivity for rubella at baseline.

## JE Per-Protocol Analysis Set (JE-PP)

The JE-PP analysis set will be based on participants who meet all of the following criteria:

- Fulfilled the eligibility (inclusion/exclusion) criteria.
- Received all study vaccines as assigned.
- Provided a valid JE serology laboratory result at baseline and at 28 days postvaccination with CD-JEV vaccine, with specimens taken within the windows indicated in Table 1.
- Did not take any prohibited concomitant medication within 28 days post-vaccination.
- Did not show seropositivity for JE at baseline.

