## **7.8. Follow-up visit 58 Days After Enrollment**

### **7.8.1. Group 2 Visit to Assess Safety 2 Days After CD-JEV (D58+3)**

1. The parents will be called to check on the welfare of the child and ensure the diary card is being completed.
2. The parents will be asked if the child experienced any other adverse reaction or SAE and/or sought medical care.
3. The parents will be reminded of their appointment to visit the clinic 14 days after vaccination (+3 days) for a follow-up visit.
4. Parents will be reminded to seek medical care as appropriate and inform the study clinician as soon as possible in the event of an adverse reaction or SAE. If the child visits a health care provider, the parents should be sure to inform him/her of the child's participation in the study and present the provider with contact information for the investigator as indicated on the study identification card. Additionally, the parents will be reminded to inform the study clinician that the child has visited a health care provider.

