**Table 4. Group 2 Allowable Schedule**

Study Visit	Should occur	May occur
Visit 0 (screening and consent)	On or before D0	Within 2 weeks of visit 1
Visit 1 (eligibility, blood draw, MMR vaccination)	Day 0	on Day 0
Visit 2 (MMR follow-up)	Day 2	2 to 5 days after MMR vaccination
Visit 3 (MMR follow-up)	Day 14	14 to 17 days after MMR vaccination
Visit 4 (MMR follow-up)	Day 28	28 to 35 days after MMR vaccination
Visit 5 (MMR blood draw, CD-JEV vaccination)	Day 56	56 to 63 days after MMR vaccination
Visit 6 (CD-JEV follow-up)	Day 58	2 to 5 day after CD-JEV vaccination
Visit 7 (CD-JEV follow-up)	Day 70	14 to 17 days after CD-JEV vaccination
Visit 8 (CD-JEV blood draw, MMR vaccination)	Day 84	28 to 35 days after CD-JEV vaccination
Visit 9 (MMR follow-up)	Day 86	2 to 5 days after MMR vaccination
Visit 10 (MMR follow-up)	Day 98	14 to 17 days after MMR vaccination
Visit 11 (final assessment)	Day 112	28 to 35 days after MMR vaccination

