#### 11.2.3.4. JE Per-Protocol Analysis Set (JE-PP)

The JE-PP analysis set will be based on participants that meet all of the following criteria:

- Fulfilled the eligibility (inclusion/exclusion) criteria set forth in Sections 5.1. and 5.2.
- Received all study vaccines as assigned.
- Provided a valid JE serology laboratory result at baseline and at 28 days post-vaccination with CD-JEV vaccine, with specimens taken within the windows prescribed by Section 7.14.
- Did not take any prohibited concomitant medication within 28 days post-vaccination.
- Did not show seropositivity for JE at baseline.

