Baseline serology will be tested for antibodies to JE, measles, mumps, rubella, and dengue virus. Antibody responses to CD-JEV will be tested 28 (+7) days after vaccination, while antibody responses to the first dose of MMR will be tested 56 (+7) days after vaccination. Specifically, antibodies to measles, mumps, and rubella will be tested on Day 0 and Day 56 (+7) for both Group 1 and Group 2; antibodies to JE will be assessed on Day 0 and Day 28 (+7) for Group 1 and on Day 56 (+7) and Day 84 (+7) for Group 2; antibodies to dengue will be tested on Day 0 for Group 1 and on Day 56 (+7) for Group 2. All laboratory testing will be conducted in a blinded fashion.

Except for a screening visit which may occur on Day 0 or before, a total of 9 visits is planned for participants in Group 1 and a total of 11 visits is planned for participants in Group 2. The duration of study participation for each participant is 4 months. The duration of the study is expected to be 7 to 8 months, dependent upon the duration of enrollment period. The schedule of study visits and activities is presented in Table 1 below.

The study will be conducted at Putatan Health Center and Bayanan Health Center located within the study area of the Research Institute for Tropical Medicine, Manila, Philippines.

	Group 1									
	efore D0	D0	D2 (+3)	D14 (+3)	D28 (+7)	D56 (+7)	D84 (+7)	D86 (+3)	D98 (+3)	D112 (+7)
Obtain informed consent	x									
Collect baseline demographic information		х								
Collect/review medical history		х								
Perform physical examination		х		x	x	х	х		х	x
Check/confirm inclusion/exclusion criteria		х								
Collect serum for serology testing		х			x	х				
Administer dose of MMR		х					х			
Administer dose of CD-JEV		х								
Observe for immediate reactions for 30 minutes		х					х			
Provide diary card to parent/guardian		х					х			
Call participant to inquire about child's well-being			x					х		
Collect diary card and review reported adverse events				x					х	
Record reported adverse events		х			x	x	х			x
Record reported serious adverse events		х	x	x	x	x	х	х	х	x
Exit participant from study										х

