#### 3.1.3. Per-Protocol Analysis Set

The Per-Protocol (PP) sets will include the participants in the ITT set who are compliant with the protocol. This data set will be used for immunogenicity analysis only. The antigen specific PP sets are defined as follows.

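### Does the SAP's JE per-protocol set drop correctly timed Group 2 samples by taking its window from Table 1?

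*SAP*

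**What the plan says.** The protocol's JE per-protocol set (11.2.3.4) requires baseline and post-dose JE results "with specimens taken within the windows prescribed by Section 7.14". In that section, Table 4 allows Group 2's CD-JEV dose "56 to 63 days after MMR vaccination" and the JE draw "28 to 35 days after CD-JEV vaccination". The same row gives Day 84 as the day on which the visit should occur.

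The SAP's JE per-protocol set (3.1.3) instead requires a result at "28 days postvaccination with CD-JEV vaccine, with specimens taken within the windows indicated in Table 1". In Table 1 the Group 2 draw stands under the column D84 (+7).

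SAP 2.2 first gives the general rule, "Antibody responses to CD-JEV will be tested 28 (+7) days after vaccination". It then lists the particular days for JE antibodies, including "on Day 56 (+7) and Day 84 (+7) for Group 2". The opening of SAP 3.1.3 describes the per-protocol sets as "participants in the ITT set who are compliant with the protocol".

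**The concern.** The two definitions cite different sources for the window, and the SAP never refers to Section 7.14. A programmer working only from the JE-PP bullet and the Table 1 column heading could code the Group 2 window as study days 84 to 91. An infant given CD-JEV late but within its window, and then bled on time relative to that dose, could fall outside. Group 1 has no such exposure, because its CD-JEV is given on Day 0.

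The per-protocol set is the primary approach to immunogenicity, so JE-PP carries the JE seropositivity difference and the GMT ratio. Under the fixed-day coding, membership would depend in one arm on how late a post-randomization dose was given. That costs precision and is an undesirable kind of selection.

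**Working it through.** **1. Where the label D84 comes from.** Nominal CD-JEV day plus nominal interval: 56 + 28 = 84, with tolerance +7. The label is therefore the protocol's 28-to-35-day window for an infant dosed exactly on D56. Protocol Table 4 shows this by setting Day 84 beside the window counted from CD-JEV.

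**2. What a fixed-day reading would lose.** For CD-JEV on day 56 + v (v = 0 to 7), the protocol-valid draw days run from 84 + v to 91 + v. Days beyond D91 number v out of 8.

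| CD-JEV day | Protocol-valid draw days | Valid days after D91 |
|---|---|---|
| D56 | D84–D91 | 0 of 8 |
| D57 | D85–D92 | 1 of 8 |
| D58 | D86–D93 | 2 of 8 |
| D59 | D87–D94 | 3 of 8 |
| D60 | D88–D95 | 4 of 8 |
| D61 | D89–D96 | 5 of 8 |
| D62 | D90–D97 | 6 of 8 |
| D63 | D91–D98 | 7 of 8 |

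The affected days are D92 to D98. In Group 1 both sources give D28 to D35, so nothing is lost. Neither document gives a distribution of visit timing, so the share of infants is unknown. It is 0% if every dose is on D56 and 28/64 = 43.75% if both delays are assumed uniform and independent.

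**3. Does the SAP support fixed study days?** Three checks say no.

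- *The sentence itself.* It places the result 28 days after CD-JEV. A fixed D84 to D91 window would admit samples taken too early: with a dose on D63, a draw on D84 is 84 − 63 = 21 days after it. The fixed-day reading thus contradicts the clause it is meant to interpret.
- *SAP 2.2.* The rule is 28 (+7) days after vaccination, and D84 (+7) follows as its instance for Group 2. The anchor is the dose and the tolerance is 7 days, which gives 28 to 35 days, as in Protocol Table 4.
- *The rest of Table 1.* CD-JEV is allowed at D56 (+7), that is to D63. The call after that dose is at D58 (+3). As fixed days the call window closes on 58 + 3 = D61, before a permitted dose on D62 or D63. Group 1 shows the same: the second MMR may be given up to 84 + 7 = D91, while the call after it would close on 86 + 3 = D89. These labels make sense only as nominal visits counted from the dose they follow. Protocol 7.8.1 says so for the D58 contact, which it describes as two days after CD-JEV.

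**4. Size if the fixed-day reading were coded anyway.** Assumptions: a JE seropositivity rate of 90% in both groups (the earlier Philippine trial in Protocol Table 2 shows 90.5% and 90.6% at Day 28 in its concomitant and measles-first groups), and 314 × 0.8 = 251 evaluable per group, borrowing the 20% non-evaluable rate stated for day 56. Half-width = 1.96 × √(0.09/251 + 0.09/n₂):

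| Group 2 loss | n₂ | Half-width (points) |
|---|---|---|
| 0% | 251 | 5.25 |
| 10% | 226 | 5.39 |
| 25% | 188 | 5.67 |
| 44% | 141 | 6.19 |

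The cost up to 44% is 6.19 − 5.25 = 0.94 points. Only if every Group 2 infant were dosed on D63 and draws were spread evenly would 7/8 be lost. Then n₂ = 251/8 ≈ 31, and the half-width is 1.96 × √(0.000359 + 0.002903) = 11.2 points. Nothing in the documents suggests that pattern.

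**The case for a change.** The best case for a change is that the one clause defining the JE-PP window points to Table 1 and nowhere else, and a set definition should not need inference from other sections. The same label, D84 (+7), also appears for Group 1, where it does mean D84 to D91 from Day 0, and the SAP has no note that the anchor differs in Group 2. The protocol heads this visit as 84 days after enrollment. Study statisticians are unmasked (Protocol 5.3.2) and JE is analyzed first, so an inclusion rule that can be read two ways in one arm is better closed beforehand, at the cost of one sentence.

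Part of this stands. The cross-reference is looser than the protocol's, and a pointer to Section 7.14 would be harmless tidying. The rest does not carry. The anchor is stated in the very sentence at issue. The Group 1 label fits the general pattern, because each label counts from the dose that governs the visit. The enrollment-style heading proves little, since the protocol heads the D58 contact the same way while tying it to CD-JEV. To lose the D92 to D98 samples and still respect the 28-day wording, an analyst would have to apply two windows at once, one from the dose and one from enrollment, and no SAP sentence asks for that.

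**Conclusion.** The difference in cross-reference is real but leaves nothing for the analysis to repair. Read together, SAP 2.2, the JE-PP sentence, Table 1's own columns and the requirement of compliance with the protocol give a draw 28 to 35 days after the actual CD-JEV date in both groups, the same as Section 7.14. An analyst using the recorded dose and draw dates arrives at the protocol's set, so the expected effect on results is nil.

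The exposure is also narrow. The JE comparisons are secondary and have no success margin. The measles, mumps and rubella windows are D56 to D63 in both documents. The supportive ITT analysis has no sampling-window criterion and would partly reveal any misapplied exclusion. The precision figures rest on the assumed 90% rate, the 251 per group and the chosen loss fractions. The conclusion does not rest on them, because it follows from the text.

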## **3.2.** Adjustment for Covariates

No adjustments for covariates are planned for the primary analysis. For the comparison of ant-measles and anti-rubella GMCs and anti-JE GMT between treatment groups, baseline antibody concentration/titer will be included in the analysis as covariate. In addition, age prior to vaccination with CD-JEV will be evaluated for inclusion as covariate for the comparison of anti-JE GMT between study groups.

#### **3.3. Missing Data and Outliers**

#### 3.3.1. Missing Data

All descriptive statistics will be performed on subjects with available data. Nonmissing serology data are considered validated. Missing serology data are considered non-retrievable. Missing serology data will not be imputed and will be analyzed as if they were randomly missing.

If severity or relationship to a study vaccine for a reported adverse event (AE) or serious adverse event (SAE) is missing, an independent category "Missing" will be reported.

If start date associated with a reported concomitant medication, AE or SAE is incomplete or missing, the following rules will be applied:

- If the day of the date is missing, use the day of the date of vaccination if start month and year are the same as those of date of vaccination; otherwise use the 15th day of the month.
- If either month or year is missing, no imputations will be done.

If stop date for a concomitant medication, AE or SAE is incomplete or missing, the medication will be considered ongoing.

If date of withdrawal/study completion is completely missing, it will not be imputed.

If date of study vaccination is incomplete or missing, the following rules will be applied:

- If day is missing, use the day of the corresponding visit at which the vaccination is scheduled if start month and year are the same as those of date of the corresponding visit; otherwise use the 15th day of the month.
- If either month or year is missing, no imputation will be done.

#### 3.3.2. Outliers

No data will be excluded from the primary and secondary analyses, including any outliers. Transformation on antibody responses during analysis can reduce the impact of the outliers. For continuous immunogenicity measures, non-parametric comparisons may be used as a sensitivity analysis if necessary.

#### 3.4. Data Handling Conventions and Transformations

For Group 1, baseline antibodies to measles, rubella, mumps, JE, and dengue will be tested on Day 0. For Group 2, baseline antibodies to measles, rubella, and mumps will be assessed on Day 0 and baseline antibodies to JE and dengue will be tested on Day 56.

The antibody concentrations/titers to measles, rubella, JE, and dengue will be transformed using log10 transformation. Data will be back-transformed to the original scale for presentation.

Numerical numbers will be presented to one decimal place if applicable.

#### **3.5. Multicenter Studies**

The primary and secondary analyses will not be adjusted by site.

#### 3.6. Multiple Comparisons/Multiplicity

No multiplicity adjustments will be performed as we expect to show if both co-primary objectives will be achieved at the same time.

#### **3.7. Timing of Analyses**

No formal interim analysis will be performed for this study. Due to an expected delay in MMR testing, JE testing will be completed first. According to this order of available serology testing results, two independent final analyses will be conducted stepwise as follows:

- The first final analysis will include all safety data and JE immunogenicity results. The estimates of the JE immunogenicity endpoints and safety endpoints and statistical tests associated with relevant secondary objectives and exploratory objective will be provided. This analysis will be performed after anti-JE antibody results are available and database is cleaned and locked at the end of the study.
- The second final analysis will included all MMR immunogenicity results. The estimates of the MMR-related immunogenicity endpoints and statistical tests associated with primary and relevant secondary objectives will be presented. This analysis will be performed as soon as MMR results are available, cleaned, and locked.

#### 4. Subject Disposition

#### 4.1. Subject Enrollment

The number of subjects screened and the number of subjects excluded will be tabulated. The number of subjects randomized will be tabulated by study group.

#### **4.2. Disposition of Subjects**

Subject disposition will be summarized by study group. The following information will be tabulated.

- The number and proportion of subjects in ITT, PP, and safety analysis sets.
- The number and proportion of subjects who were randomized but received no vaccines.
- The number and proportion of subjects who are excluded from the ITT analysis and reasons for exclusion.
- The number and proportion of subjects who are excluded from the PP analysis and reasons for exclusion.
- The number and proportion of subjects who completed the study visit.
- The number and proportion of subjects who have blood collection done at each applicable visit.
- The number and proportion of subjects who have valid serology results at each applicable visit.

Listings of subject disposition and status, exclusions from the ITT analysis, exclusions from the PP analysis, and exclusions from the safety analysis will be provided.

## 4.3. Withdrawals of Subjects

Participants may withdraw from the study at any time and for any reason. The investigator may withdraw participants from the study for various reasons. The number of withdrawals and the reasons for the withdrawals will be summarized by study group.

## 5. Subject Characteristics

## 5.1. Baseline Characteristics

Demographic and baseline characteristics including age, gender at birth, weight, and height will be summarized by study group for the ITT and PP populations. Age will be calculated in months rounding to the precision of one decimal place using the following formula:

Age (months) = [(Date of Day  $0 - Date of Birth) \ge 12]/365.25$ 

Age, weight, and length will be described by number of subjects with data, mean, standard deviation (SD), median, minimum, and maximum. Gender at birth will be described by number and proportion of subjects in each study group. Denominators for proportions will be the number of subjects with non-missing values. In order to confirm whether study groups of our interest are similar in terms of demographic and baseline characteristics, T-test will be used to compare age, weight, and length and Fisher's Exact Test will be used to compare gender at birth.

In addition, vital signs, immunization history, medical history, pre-existing conditions, and physical exam collected on Day 0 will be summarized by study group.

Baseline serology results in terms of antigen-specific seropositivity will be provided as part of the immunogenicity results. In addition, GMCs/GMT for the antibody concentrations/titers to measles, rubella, JE, and dengue will be provided at baseline as well.

#### 5.2. Subject Characteristics at Each Visit

Vital signs (height, weight, axillary temperature, respiratory rate, blood pressure, pulse rate, weight for height z-score < -3 (yes or no) and physical exam (general appearance, head, eyes, ears, nose, throat, lymph nodes, cardiovascular/heart, respiratory/lungs, abdomen, musculoskeletal/extremities, skin, neurological/central, endocrine, health status) collected at other visits will be summarized for ITT population by study group.

Listings of demographics, immunization history, medical history, pre-existing condition, vital signs, and physical exam at each applicable time point will be provided at participant level.

#### **5.3.** Concomitant Medications

Concomitant medications collected during study will be summarized in terms of anatomical therapeutic chemical (ATC) classification and preferred drug name for the ITT population by study group. The preferred drug name, ATC classification, route, dose, units, frequency, start and stop dates, and duration of the medications will be listed at participant-level.

The duration of a concomitant medication will be computed as follows:

Duration (days) = Stop Date - Start Date + 1

If the stop date is completely missing, the particular medication will be considered to be ongoing and the duration will not be calculated.

#### 6. Immunogenicity Analyses

Immunogenicity analyses will primarily be performed on PP analysis set. Supportive immunogenicity analyses will also be conducted on ITT analysis set.

## 6.1. Primary Immunogenicity Endpoints

• Proportion (or percentage) of participants with demonstrated seropositivity for measles at 56 days post-vaccination. Seropositivity will be defined as a post-

vaccination concentration of  $\geq$  120 mIU/mL, as measured by PRNT (using the 3rd International Standard Reference serum to convert dilutions to concentrations).

Proportion (or percentage) of participants with demonstrated seropositivity for rubella at 56 days post-vaccination. Seropositivity will be defined as a postvaccination concentration of  $\geq 10$  IU/mL (corresponding to an OD ratio  $\geq 1.10$ using a commercial ELISA manufactured by Wampole Laboratories, Princeton, NJ).

## **6.2.** Analysis of Primary Immunogenicity Endpoints

## **Primary Hypotheses**

To demonstrate the non-inferiority of MMR vaccination in terms of measles and rubella immunogenicity when administered concomitantly with CD-JEV to infants 9 months of age compared to administration alone, the following co-primary hypotheses will be tested:

H0M: (P(M1) minus P(M2))  $\leq -10\%$  $H_{1M}$ : (P(M1) minus P(M2)) > -10% H0R:  $(P_{(R1)} minus P_{(R2)}) \le -10\%$ 

and

 $H_{1R}$ : (P(R1) minus P(R2)) > -10%

where  $P_{(M1)}$  refers to the percentage of participants with seropositivity for measles in Group 1 and P(M2) refers to the percentage of participants with seropositivity for measles in Group 2 and where  $P_{(R1)}$  refers to the percentage of participants with seropositivity for rubella in Group 1 and  $P_{(R2)}$  refers to the percentage of participants with seropositivity for rubella in Group 2.

## **Analysis Methods**

The proportion of participants with seropositivity for measles and rubella at 56 days postvaccination will be presented with exact 95% CI using Clopper-Person method by study group.

The comparison between Group 1 and Group 2 will be tested for non-inferiority. Noninferiority will be achieved when both  $H_{0M}$  and  $H_{0R}$  are rejected, that is, if the lower limit of the two-sided 95% CI for the difference in percentages of participants with seropositivity (concurrent administration minus separate administration) at 56 days post-vaccination is > -10% for both measles and rubella results. The 95% CI will be calculated using Farrington-Manning score method.

